8.2 Final Analysis Plan

The results of this pilot trial will be used to assess the feasibility and inform the design of the definitive trial. We will present point estimates of feasibility events, including enrolment, adherence to protocol and accrual, as proportions with 95% confidence intervals. We will present continuous data as means and standard deviations, or medians and inter-quartile ranges, as appropriate.

An intention-to-treat analysis will be performed on all patients randomized for the secondary efficacy outcome. A per protocol analysis will be conducted for patients who have taken at least 90% of the

prescribed doses. Subgroup analysis will be performed on the stratified groups with hemoglobin 100g/L or greater and hemoglobin less than 100g/L. Additional subgroup analyses will include: patients with ongoing bleeding (WHO grade 2 or higher) vs no bleeding; and normal vs. increased CRP (based on the normal range).

8.3 Interim analysis

Safety and interim analyses will be performed after enrolling 20 patients to the study.

8.4 Stopping Rules

This study will be stopped prior to its completion if: (1) difficulty in study recruitment or retention will significantly impact the ability to evaluate the study endpoints; or (2) any new information becomes available during the trial that necessitates stopping the trial.

9.0 ASSESSMENT OF SAFETY

9.1 Definitions

9.1.1 Adverse Event

An **Adverse Event (AE)** is defined as any new event that may jeopardize the patient which the study investigator physician perceives may be directly related to the enrolment in the pilot study or to the assigned arm. Adverse events are not study related if they are related primarily to the underlying disease. All AEs are to be documented and assessed for relatedness. If related to the study drug and occurring from baseline up to one week after the final study visit, the AE will be recorded on the eCRF and coded as per the most recent edition of the Common Terminology Criteria for Adverse Events (CTCAE).

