5.4.2.4 Week 12 Final Study Visit

Participants will be assessed in person/remotely (telephone/zoom/OTN) at Day 84 ± 7 days for the following assessment

- Adherence as determined by patient diary and pill count
- Side effect questionnaire
- FACIT-fatigue scale questionnaire
- Medication history (to confirm if any new or discontinued medications)
- Laboratory tests: CBC, reticulocyte count, ferritin, serum iron and TSAT
- Need for escalation in therapy: Y/N
 - Increase in oral iron regimen from every other day to daily
 - Intravenous iron
 - Transfusion
 - Visit to emergency department related to anemia

5.4.2.5 Week 13

Participants will be contacted by telephone or email at $7 \text{ days} \pm 3$ days after the Week 12 final study visit for assessment of adverse and serious adverse events.

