9.1.2 Expected adverse events with ferrous sulfate

Side effects of oral iron supplementation include constipation, nausea, diarrhea, abdominal pain, vomiting, heartburn, flatulence and dark stools.^{8,35} When compared to placebo in randomized controlled trials, ferrous sulfate had an increased incidence of gastrointestinal (GI) side effects with an OR 2.32 (95% CI 1.74-3.08). The proportion of patients with GI side effects was 35% (range 10-90%) in the ferrous sulfate arms compared with 22% (range 0-69%) in the placebo arms. The most common side effects were constipation, nausea and diarrhea with pooled estimates of incidence of 12%, 11% and 8% respectively.³⁵ Additional side effects included abdominal pain, vomiting, heartburn, flatulence and dark stools.

Overall, the risk to patients enrolled in this study is anticipated to be low, as 1) patients with IDA would normally be treated with oral iron; 2) patients with a prior history of intolerance to oral iron will be excluded; 3) exclusions include patients with baseline gastrointestinal disease such as inflammatory bowel disease; 4) patients will be monitored for side effects throughout the study; and 5) side effects stop immediately with stopping oral iron with no long term sequelae.

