9.1.5 Serious Adverse Event (SAE)

A serious adverse event (SAE) in the study is defined as:

- a) any event that is fatal or immediately life threatening, permanently disabling, severely incapacitating, or requires prolonged inpatient hospitalization, or
- b) any event that may jeopardize the patient and requires medical or surgical intervention to prevent one of the outcomes listed above, AND
- c) which the attending physician perceives may be directly related to enrolment in the study, or to the assigned arm.

SAEs will be considered to be study-related if the event follows a reasonable temporal sequence from the study intervention and could readily have been produced by the intervention. Adverse events are not study related if they are related primarily to the underlying disease.

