9.2.5 Adverse Event Recording

Investigations into potential adverse events should be done during each contact with a participant.

Investigations may be done through specific questioning and, as appropriate, by examination.

Information on all adverse events should be recorded promptly in the source document, and assessed by an investigator in a timely manner allowing sufficient time to meet required reporting timelines for SAEs and serious unexpected adverse drug reactions (SUADRs) if needed. Adverse event CRFs should be completed using source documents by a delegated research team member in a timely manner/within 15 days of site awareness. All clearly related signs, symptoms, and abnormal diagnostic procedures should be recorded in the source document, though should be grouped under one diagnosis. Each diagnosed adverse event should then be categorized in accordance with the revised NCI Common Terminology Criteria for Adverse Events (CTCAE).

The following are not considered AEs and therefore do not require recording:

- Pre-existing diseases or conditions identified and recorded at screening/baseline unless, at the discretion of the investigator, the disease or condition worsens in severity or frequency
- At the discretion of the investigator, events considered likely manifestations of the underlying disease or that commonly occur in the study population independent of study drug exposure
- Elective medical or surgical procedures.

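### Read literally, the adverse event definition in 9.1.1 excludes the expected gastrointestinal events listed in 9.1.2, so they need not be recorded, graded or assessed for causality as AEs, although the side effect questionnaire still collects them

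*Combined protocol and SAP*

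**What the plan says.** Section 9.1.1 (Adverse Event) states that an AE "is defined as any new event that may jeopardize the patient which the study investigator physician perceives" as one that "may be directly related to the enrolment in the pilot study or to the assigned arm". It continues: "All AEs are to be documented and assessed for relatedness". For events related to study drug, from baseline to one week after the final visit, "the AE will be recorded on the eCRF and coded as per the most recent edition" of CTCAE.

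Section 9.1.2, whose heading calls its contents expected adverse events, says: "Side effects of oral iron supplementation include constipation, nausea, diarrhea, abdominal pain, vomiting, heartburn, flatulence and dark stools". Section 9.1.3 defines an unexpected AE as one not identified in 9.1.2 or in the product monograph.

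Section 9.1.5 uses the jeopardy wording again in limb (b) of the SAE definition: "any event that may jeopardize the patient and requires medical or surgical intervention to prevent one of the outcomes listed above".

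Section 9.2.5 removes pre-existing conditions from AE recording "unless, at the discretion of the investigator, the disease or condition worsens in severity or frequency".

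Side effects also have a separate route. Section 5.4.2 schedules a side effect questionnaire at weeks 1, 4, 8 and 12. Section 7.2 defines outcomes on step-down in therapy (8), side effects by questionnaire (14) and stopping iron because of side effects (15). The Week 13 contact (5.4.2.5) takes place "after the Week 12 final study visit for assessment of adverse and serious adverse events" and has no other purpose.

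**The concern.** The entry condition for any AE is written in language that 9.1.5 uses for seriousness. The known harms of oral iron are mostly uncomfortable rather than dangerous, so a literal reader of 9.1.1 can leave them off the AE form. Another reader, guided by 9.1.2, will record them. The number of AEs then depends partly on how each investigator understands jeopardy, and those investigators know the treatment arm because the trial is open-label.

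This matters because section 2.2 gives fewer side effects as part of the rationale, section 8.3 plans a safety analysis after 20 patients, and section 9.4 dispenses with a DSMB. Events that never become AEs receive no CTCAE grade and no causality assessment. It also becomes harder to notice an expected reaction that is unexpected in severity or frequency, which 9.1.3 and 9.2.2 treat as a reason to reclassify it.

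**Working it through.** The plan states no figure on this point, so the check sets the sections side by side. The arithmetic at the end is for scale only.

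**1. Conditions in 9.1.1.** Three must hold together: the event is new, it may jeopardize the patient, and the investigator perceives possible relatedness to enrolment or arm. An investigator would usually accept that constipation or nausea on iron may be related. For these events the jeopardy condition is therefore the one that excludes them.

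**2. Agreement with the rest of section 9.**

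| Section | What it implies | Fit with 9.1.1 |
|---|---|---|
| 9.1.2 | Constipation, nausea, flatulence, dark stools and similar are expected AEs | Conflicts: such events seldom jeopardize a patient |
| 9.1.3 | The events in 9.1.2 are AEs of the expected kind | Conflicts, for the same reason |
| 9.2.4, 9.2.5 | AEs are graded and categorized by CTCAE; severity may be mild | Conflicts: a jeopardy test leaves little for the mild end |
| 9.2.5 | A pre-existing condition that worsens remains an AE | Not clearly covered by a definition limited to new events |
| 9.1.5(b) | Jeopardy plus a need for intervention makes an event serious | Part of a seriousness test serves as the AE entry test |

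**3. Whether 9.2.5 repairs it.** Its duty to record covers all adverse events, but 9.1.1 decides what counts as one. Its list of non-recordable events does not name drug-related GI effects, which favours recording them but does not override the definition.

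**4. What is collected anyway.** The questionnaire is listed at weeks 1, 4, 8 and 12 in 5.4.2. The Appendix C row, as it reads in the available text, marks weeks 4, 8 and 12 only. Outcome 14 uses the questionnaire at weeks 4, 8 and 12; outcomes 8 and 15 use step-down and stopping. Appendix C keeps the questionnaire and adverse events on separate rows, and no section says that a questionnaire answer becomes an AE entry, is graded or is assessed for causality.

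**5. What is left exposed.**
- The AE eCRF and its CTCAE coding.
- The safety analysis after 20 patients, so far as it uses that eCRF. Section 8.3 names no data source.
- Events reported at Week 13, where AE inquiry is the only assessment.
- Reactions outside the questionnaire. Section 2.1.6 describes the parent instrument as distinguishing GI symptoms. The trial's modified version is not in the documents.

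**6. Scale.** Inputs are 52 patients, 26 per arm (5.1), and GI side effects in 35% on ferrous sulfate, range 10–90% (9.1.2). Expected patients = N × rate.
- All patients: 52 × 0.35 = 18.2, about 18
- Per arm: 26 × 0.35 = 9.1, about 9
- First 20 patients: 20 × 0.35 = 7
- Range: 52 × 0.10 = 5.2 to 52 × 0.90 = 46.8, about 5 to 47

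This applies one pooled rate to both arms, although one arm takes half the doses.

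**The case against.** The best reply is that section 9 read as a whole points towards recording. Sections 9.1.2 and 9.1.3 treat the events as AEs, 9.2.5 calls for inquiry at every contact and for related signs and symptoms to go into the source document, and CTCAE has mild grades. A sensible investigator may well record them. That is fair as a forecast of behaviour, but it leaves the governing definition saying something else.

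A reader might go further and infer that these side effects need not be recorded at all, or that the proportion with an AE could fall anywhere between near zero and 35%. The documents do not support either inference. The questionnaire and outcomes 8, 14 and 15 require the effects to be collected, and 2.1.6 asks for careful documentation. The lower end of that range is only the extreme literal reading, and the upper end is a pooled rate whose own range is 10–90%.

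Three narrower objections also carry weight:
- A worsening can be read as a new event, so the conflict over newness is the weaker one.
- Limb (b) of 9.1.5 also requires intervention, so jeopardy alone is not the full SAE threshold.
- The Week 13 gap is probably small, since treatment ends at week 12 and 9.1.2 expects side effects to stop when iron stops.

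Finally, correcting the definition alone would leave the link from questionnaire to AE form unstated. That stands, and the fix includes it.

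**Conclusion.** The definition is wrong as written, with a bounded consequence. Read literally, 9.1.1 excludes events that 9.1.2 and 9.1.3 treat as adverse events, so they need not be entered, graded or assessed for causality as AEs. The tolerability comparison does not depend on that record, because it rests on the questionnaire, step-down and stopping data. The loss is confined to the four exposed parts listed in the working.

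If the pooled rate applied to both arms, about 18 of 52 patients would have events of this kind, or about 5 to 47 over the quoted range. These are patients whose GI events could be missing from the AE record. They are not a forecast of how many would be missing, and the questionnaire would still reach them. Whether non-GI reactions have another route cannot be settled without the modified questionnaire.

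The relatedness condition in 9.1.1, which anticipates the relatedness assessment required in the same paragraph, is a separate matter and not needed for this conclusion.

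**What to change.** - In 9.1.1, delete the clause requiring that the event may jeopardize the patient, and replace *any new event* with *any new or worsened unfavourable sign, symptom or diagnosis after enrolment*.
- Keep the jeopardy wording only in 9.1.5(b), where it helps to define seriousness, and let the CTCAE grade carry severity.
- Add one line stating how a positive questionnaire response is entered in the AE record, so that it is graded once and not counted twice.

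The cost is a wording amendment and more AE forms to complete. No visit or test is added.

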9.1.2 Expected adverse events with ferrous sulfate

Side effects of oral iron supplementation include constipation, nausea, diarrhea, abdominal pain, vomiting, heartburn, flatulence and dark stools.^{8,35} When compared to placebo in randomized controlled trials, ferrous sulfate had an increased incidence of gastrointestinal (GI) side effects with an OR 2.32 (95% CI 1.74-3.08). The proportion of patients with GI side effects was 35% (range 10-90%) in the ferrous sulfate arms compared with 22% (range 0-69%) in the placebo arms. The most common side effects were constipation, nausea and diarrhea with pooled estimates of incidence of 12%, 11% and 8% respectively.³⁵ Additional side effects included abdominal pain, vomiting, heartburn, flatulence and dark stools.

Overall, the risk to patients enrolled in this study is anticipated to be low, as 1) patients with IDA would normally be treated with oral iron; 2) patients with a prior history of intolerance to oral iron will be excluded; 3) exclusions include patients with baseline gastrointestinal disease such as inflammatory bowel disease; 4) patients will be monitored for side effects throughout the study; and 5) side effects stop immediately with stopping oral iron with no long term sequelae.

9.1.3 Unexpected Adverse Event

An unexpected adverse event is defined as any adverse event that is not identified in section 9.1.2 or in nature, severity or frequency in the current Health Canada Product Monograph.

9.1.4 Unexpected Adverse Drug Reaction (ADR)

An unexpected ADR is an adverse reaction, the severity of which is not consistent with the Health Canada Product Monograph. All noxious and unintended responses to a medicinal product related to any dose should be considered an ADR.

The phrase "responses to a medicinal product" means that a causal relationship between a medicinal product and an adverse event is at least a reasonable possibility, i.e., the relationship cannot be ruled out.

9.1.5 Serious Adverse Event (SAE)

A serious adverse event (SAE) in the study is defined as:

- a) any event that is fatal or immediately life threatening, permanently disabling, severely incapacitating, or requires prolonged inpatient hospitalization, or
- b) any event that may jeopardize the patient and requires medical or surgical intervention to prevent one of the outcomes listed above, AND
- c) which the attending physician perceives may be directly related to enrolment in the study, or to the assigned arm.

SAEs will be considered to be study-related if the event follows a reasonable temporal sequence from the study intervention and could readily have been produced by the intervention. Adverse events are not study related if they are related primarily to the underlying disease.

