9.2.3 Seriousness

Events are classified as serious if associated with effects threatening the life or physiological functions of a participant. Refer to the definition for "Serious Adverse Events" in section 9.1.5.

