9.3.2 Investigator reporting: Notifying the Sponsor

The investigator is responsible for reporting SAEs and SUADRs to the sponsor (Sunnybrook Research Institute) in accordance with applicable regulations and reporting requirements and timelines.

Events that are assessed to be **serious and unexpected and related or cannot be ruled out as related** to the investigational product are considered SUADRs. Reporting for SUADRs should include a description of the event in sufficient detail to allow for a complete medical assessment of the case and independent determination of possible causality. The minimum information required includes at least one identifiable participant, one identifiable reporter, one serious reaction, and one suspect product.

Additionally, for SAEs and SUADRS, a Suspect Adverse Reaction Report – CIOMS I Form (see appendix D) must be completed by the investigator and forwarded to the Sponsor within 24 hours of site awareness.

Information on other possible causes of the event, such as concomitant medications and illnesses should also be provided as soon as is made available.

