APPENDIX D:**Suspect Adverse Reaction Report**

CIOMS FORM

SUSPECT ADVERSE REACTION REPORT											

I. REACTION INFORMATION

1. PATIENT INITIALS (first, last)	1a. COUNTRY	2. DATE OF BIRTH	2a. AGE	3. SEX	4-6 REACTION ONSET	8-12 CHECK ALL APPROPRIATE TO ADVERSE REACTION
		Day Month Year	Years		Day Month Year	 PATIENT DIED  INVOLVED OR PROLONGED INPATIENT HOSPITALISATION  INVOLVED PERSISTENCE OR SIGNIFICANT DISABILITY OR INCAPACITY  LIFE THREATENING
7 + 13 DESCRIBE REACTION(S) (including relevant tests/lab data)						

II. SUSPECT DRUG(S) INFORMATION

14. SUSPECT DRUG(S) (include generic name)	20. DID REACTION ABATE AFTER STOPPING DRUG?  YES  NO  NA	
15. DAILY DOSE(S)	16. ROUTE(S) OF ADMINISTRATION	21. DID REACTION REAPPEAR AFTER REINTRODUCTION?  YES  NO  NA

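### Section 9.1.5 counts hospitalization as serious only if it is prolonged, while the required report form also counts admission itself, so some related short admissions fall outside SAE reporting

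*Combined protocol and SAP*

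**What the plan says.** Section 9.1.5 has three limbs. Limb (a) lists death, immediate threat to life, permanent disability, severe incapacity and hospitalization. The last three read "permanently disabling, severely incapacitating, or requires prolonged inpatient hospitalization, or". Limb (b) adds "any event that may jeopardize the patient and requires medical or surgical intervention to prevent one of the outcomes listed above, AND". Limb (c) adds a relatedness condition: "which the attending physician perceives may be directly related to enrolment in the study, or to the assigned arm".

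Section 9.2.3 gives a general description, "Events are classified as serious if associated with effects threatening the life or physiological functions of a participant", and then refers the reader to 9.1.5 for the definition.

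Section 9.3.2 says that, for SAEs and SUADRs, "a Suspect Adverse Reaction Report – CIOMS I Form (see appendix D) must be completed by the investigator"; it is due at the sponsor within 24 hours of site awareness. Two of the tick boxes on that form read "INVOLVED OR PROLONGED INPATIENT HOSPITALISATION" and "INVOLVED PERSISTENCE OR SIGNIFICANT DISABILITY OR INCAPACITY".

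Section 9.3.5 gives the sponsor-reporting limits: 24 hours for deaths and immediately life-threatening events, and 72 hours for other SAEs. Adverse events in general need only be entered in the CRF, within 15 days.

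**The concern.** The definition that decides whether an event is serious is narrower on hospitalization than the form used to report serious events. On the form, being admitted is enough. In 9.1.5 the stay must also be prolonged, and no length or reference point is given. Two sites could class the same two-night stay differently and both could claim to follow the protocol.

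What is at stake is the reporting route. An event classed as non-serious does not trigger a prompt report to the sponsor. A SUADR must be serious by the definition in 9.3.2, so the event also cannot reach the notices to Health Canada and to the other site in 9.3.3 and 9.3.4. It would be absent from the SAE count taken into the definitive trial. Section 9.4 dispenses with a DSMB, which makes correct classification at the site matter somewhat more.

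**Working it through.** No arithmetic settles this point. The check is a comparison of the passages, followed by tracing one event through them.

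**Step 1: the two lists side by side.**

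| Criterion | Section 9.1.5 | Appendix D form |
|---|---|---|
| Death | yes | yes |
| Threat to life | yes, if immediate | yes |
| Disability or incapacity | permanent disability, or severe incapacity | persistent or significant disability or incapacity |
| Hospitalization | only if prolonged | involved or prolonged |
| Intervention to prevent a listed outcome | yes, limb (b) | no separate box |

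The hospitalization row is a clear mismatch. The disability row is a smaller one: permanent is narrower than persistent or significant, but 9.1.5 has severe incapacity beside it, which covers part of the difference.

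**Step 2: which text governs.** Section 9.2.3 sends the site to 9.1.5 and names no admission criterion of its own. Section 9.3.2 calls for the form once there is an SAE or SUADR. Section 9.3.5 sets time limits for events already classed as SAEs. The wider box therefore comes into play after classification and cannot bring in an event that 9.1.5 has left out.

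**Step 3: one event traced.** Take an event that the physician thinks may be related to the study, with a short admission, no immediate threat to life, no disability and no severe incapacity.

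- Limb (a): not met, because the stay was not prolonged.
- Limb (b): met only if an intervention was needed to prevent an outcome in limb (a). An ordinary admission is not one of those outcomes. Suppose no listed outcome was in prospect; then limb (b) is not met.
- Limb (c): met, but it is an added condition and cannot make the event serious alone.
- Result: not an SAE.

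**Step 4: the consequence for that event.** The sponsor report due within 24 hours (9.3.2) or 72 hours (9.3.5, if not fatal or immediately life threatening) is not triggered. There is no SUADR assessment. If the event is judged related to the study drug, section 9.1.1 puts it on the eCRF, where 9.3.5 allows 15 days.

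**Assumption.** I read limb (c) as qualifying both (a) and (b). If it qualifies only (b), relatedness no longer limits limb (a), and the hospitalization gap would also include short admissions judged unrelated. The mismatch is there on either reading.

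**The case against.** The form is a reporting template, not the protocol's definition of seriousness, and 9.1.5 is wider than its hospitalization wording suggests. Many admissions would qualify under another criterion: immediate threat to life, severe incapacity, or an intervention that brings in limb (b). This stands, and it limits the point to the remainder. It does not remove the mismatch, since no passage makes admission itself a criterion. The general description in 9.2.3 could be stretched to cover some of these cases, but it defers to 9.1.5.

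Three stronger readings are tempting, and the documents do not support them.

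- *No ordinary admission is reported as an SAE.* A reader might infer this from the hospitalization wording alone. The other criteria in limb (a), together with limb (b), catch some short admissions.
- *Admissions for worsening anemia in the every-other-day arm would be lost.* Section 9.1.5 treats events due primarily to the underlying disease as not study related, and 9.2.5 lets the investigator leave likely disease manifestations unrecorded. Rewording the hospitalization criterion may not change how such an admission is classed. Much of that signal is also collected elsewhere: intravenous iron, transfusion and anemia-related emergency visits are outcome 16, and a hemoglobin drop is outcome 17.
- *The sponsor has almost no other view of serious harm.* Section 8.3 plans a safety analysis after 20 patients, 12.1 has bi-weekly status reports and regular site meetings, and 12.2 has central review of all participants' electronic data. Section 9.3.1 also sends unanticipated events to the REB. None of these replaces a prompt SAE report, but they exist.

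A reader might also size the problem from an assumed admission rate. With 1% to 5% of 52 patients admitted for a short stay, the expected number is 52 × 0.01 = 0.52 to 52 × 0.05 = 2.6. Those rates are not in the documents. The result would count every short admission, including those that another limb catches and those judged unrelated. At those assumed rates it is at most a ceiling.

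**Conclusion.** The mismatch is real and gives a wrong classification for a defined, narrow group: possibly related events with a short admission that are not fatal, immediately life threatening, disabling, severely incapacitating or caught by limb (b). Under the plan as written these are not SAEs, so they receive neither the expedited sponsor report nor a SUADR assessment. The absence of a definition of prolonged adds room for the sites to differ.

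The size of the group cannot be estimated from the documents and is probably small in 52 patients followed for about 13 weeks. Admissions judged unrelated, or due to underlying disease, depend on the separate relatedness wording and are not claimed here. The conclusion rests on the text alone and needs no assumed rate. It should be corrected because the fault lies in a governing definition and costs almost nothing to repair.

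**What to change.** Reword limb (a) of 9.1.5 so that it agrees with Appendix D. For hospitalization, for example: *requires inpatient hospitalization or prolongs an existing hospitalization*. For disability, replace the permanent-disability wording with *persistent or significant disability or incapacity* and keep the existing severe-incapacity criterion. Elective procedures need no new exemption, because 9.2.5 already leaves them out of adverse event recording.

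Section 10.1 lists SAEs among the reasons for withdrawal, so a wider definition would also widen that trigger. The sponsor should reconcile 10.1 with the revised 9.1.5 in the same amendment; how it does so is a clinical decision for the sponsor.

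The cost is one line of definition, the check of 10.1, and possibly one or two more SAE forms over the trial. No visits, tests or staff are added.

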9.2 Assessment of an Adverse Event

9.2.1 Relationship (Causality/Relatedness)

The causality assessment is the determination, according to the investigator's clinical judgment, of the existence of a reasonable possibility that the study drug (IP) caused or contributed to an adverse event.

If the investigator or delegated sub-investigator is unsure about whether or not the study drug caused or is related to the event, then the event will be handled as "related" to the study drug for reporting purposes of the trial. If the causality assessment is "unknown but not related" to the study drug, this should be clearly documented in the source documents.

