9.3.5 Reporting and Entry Timelines

Study investigators will report SAEs to the sponsor within the following timelines:

- All deaths and immediately life-threatening events, whether related or unrelated, will be recorded and reported to the sponsor within 24 hours of site awareness.
- Serious adverse events other than death and immediately life-threatening events, regardless of relationship, will be reported to the sponsor within 72 hours of site awareness.

Adverse event information will be entered into the CRF in a timely manner and **no later than 15 days** from the time the investigator becomes aware of the event.

Serious adverse event information will be entered into the CRF in a timely manner/**within 72 hours** from the time the investigator becomes aware of the event.

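### The AE and SAE definitions (9.1.1, 9.1.5) contain a relatedness test that the SAE reporting rule (9.3.5) says does not matter, and 9.3.2 and 9.3.5 give other SAEs different sponsor deadlines

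*Combined protocol and SAP*

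**What the plan says.** All references are to the combined protocol and SAP.

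- **AE definition (9.1.1).** An AE is a new event that may put the patient at risk and "which the study investigator physician perceives may be directly related to the enrolment in the pilot study or to the assigned arm". The same section then has all AEs documented and assessed for relatedness. It sets the eCRF rule as follows: "If related to the study drug and occurring from baseline up to one week after the final study visit, the AE will be recorded".
- **SAE definition (9.1.5).** Limb (a) lists outcomes such as death, disability and prolonged hospital stay. Limb (b), joined by *or*, covers events needing intervention to prevent those outcomes. Limb (c), joined by *AND*, is an event "which the attending physician perceives may be directly related to enrolment in the study, or to the assigned arm".
- **Causality (9.2.1).** The investigator judges whether the study drug caused or contributed to the event. If the assessor is "unsure about whether or not the study drug caused or is related to the event", the event is handled as related.
- **Recording (9.2.5).** AEs go into the source document. Events thought to stem from the underlying disease may be left out at the investigator's discretion.
- **Reporting to the sponsor (9.3.5).** "All deaths and immediately life-threatening events, whether related or unrelated, will be recorded and reported to the sponsor within 24 hours". Other SAEs, "regardless of relationship, will be reported to the sponsor within 72 hours of site awareness".
- **CIOMS form (9.3.2).** For SAEs and SUADRs, without exception, the form "must be completed by the investigator and forwarded to the Sponsor within 24 hours of site awareness".

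**The concern.** A rule to report SAEs whatever their relationship only works if an event can be an SAE before anyone has decided on relationship. Here the definitions ask for that decision first.

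This matters more than usual in this design. The trial is open-label, so the judgement is made knowing the arm. Section 9.4 describes the experimental arm as the same drug at a lower dose, so a natural worry is under-treatment: an event related to the assigned schedule but not caused by the drug. Such an event also resembles the underlying disease, which is anemia, and so falls close to the discretion given in 9.2.5. Similar events could then be recorded differently by site or by arm. There is no DSMB (9.4).

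The deadline mismatch is a separate, practical matter: a site working to the longer limit can be late under the shorter one.

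**Working it through.** The plan gives no figure to reproduce, so the check compares the sections and follows events through them.

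**1. Is relatedness inside the definitions?** In 9.1.1, yes, without ambiguity. In 9.1.5 the list *a, or b, AND c* has two readings:
- Reading 1: (a or b) and c. Relatedness is required for every SAE.
- Reading 2: a or (b and c). Relatedness is required only for limb (b).

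**2. What happens to an event judged unrelated at the definition stage?**

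| Event judged unrelated | Reading 1 | Reading 2 |
|---|---|---|
| Death or immediately life-threatening | Reported under its own rule in 9.3.5 | Same |
| Other limb (a) event, e.g. prolonged hospital stay | Not an SAE by definition | SAE, reported under 9.3.5 |
| Limb (b) event | Not an SAE by definition | Not an SAE by definition |
| Non-serious event | Not an AE under 9.1.1 | Same |

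The gap is therefore in serious events that are neither fatal nor immediately life-threatening (all of them on reading 1, limb (b) only on reading 2), and in non-serious AEs on either reading. On reading 2, an unrelated limb (a) event would be an SAE under 9.1.5 without being an AE under 9.1.1, so that reading does not make the sections consistent.

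**3. What does the rest of section 9 imply?** Section 9.2.3 classifies seriousness by threat to life or function, 9.2.1 treats causality as its own step, and 9.3.2 builds a SUADR from serious, unexpected and related as three separate attributes. All three treat relatedness as something decided after an event has been identified, which the definitions do not allow.

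**4. What reaches the eCRF?** The AE definition in 9.1.1 accepts relation to enrolment or to the arm; its eCRF rule accepts only relation to the study drug. An event attributed to under-treatment can satisfy the first and fail the second. The rule in 9.2.1 that resolves doubt in favor of related also concerns only the drug as cause, so it does not help such an event.

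**5. Deadlines to the sponsor, both counted from site awareness.**
- Deaths and immediately life-threatening events: 24 h (9.3.2) and 24 h (9.3.5); difference 24 − 24 = 0 h.
- Other SAEs: 24 h for the CIOMS form (9.3.2) and 72 h for the SAE report (9.3.5); difference 72 − 24 = 48 h.

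**The case against.** The strongest reply is that the wording *may be* sets a low first screen, with causality decided later. Several places support this. Section 9.1.1 has all AEs assessed for relatedness; 9.1.5 says when an SAE counts as study-related, which presupposes some that do not; 9.2.1 provides for events of unclear cause judged not related; 9.2.5 asks for inquiry at every contact; and Appendix C schedules AE and SAE checks at weeks 1, 4, 8, 12 and 13. This stands as a plausible account of intent. It does not remove the problem: an event that fails even a low screen still falls outside the 9.1.1 definition.

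Second, worsening anemia is captured without any judgement about drug or arm, through the hemoglobin-drop and escalation outcomes (3.4, items 16 and 17) and the week 4 classification of the reason for a drop (5.4.2.2). This stands, and it limits the damage to AE and SAE records.

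Third, the two deadlines attach to differently named submissions, and meeting 24 hours satisfies both. This is true, but nothing explains why the completed form should fall due 48 hours before the report.

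Four stronger inferences are tempting but not supported:
- *An event judged unrelated can never be an AE or SAE.* This fails for limb (a) events on reading 2, and deaths and immediately life-threatening events have their own rule.
- *The eCRF rule in 9.1.1 contradicts 9.3.5.* Section 9.3.5 says "Adverse event information will be entered into the CRF in a timely manner" and sets a time limit. It is a timing rule that does not restate scope, so it does not clearly conflict.
- *The safety analysis after 20 patients rests on these records.* Section 8.3 does not say which data it uses.
- *20/52 = 38% measures the problem.* It is only the share of planned patients enrolled at that analysis.

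**Conclusion.** The concern holds as an inconsistency in the current text. Sections 9.1.1 and 9.1.5(c) place perceived relatedness inside the definitions; 9.3.5 disregards relationship, and 9.2.1 assesses causality later. Followed literally, a causality judgement made with knowledge of the arm can screen out events before they are recorded. The restriction of eCRF entry to drug-related AEs, and the discretion in 9.2.5, add to this for events tied to the assigned arm.

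The effect falls on AE and SAE records and on any safety review that uses them. Its size cannot be estimated, because the documents give no SAE or admission rate. How far it reaches among SAEs depends on which reading of 9.1.5 a site adopts; for AEs it does not. The deadline conflict is definite: 48 hours, confined to SAEs that are neither fatal nor immediately life-threatening.

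This should be corrected. It does not undermine the feasibility outcome or the listed clinical outcomes.

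**What to change.** 1. Delete the relatedness condition from the AE definition in 9.1.1 and limb (c) from 9.1.5, so that an event qualifies by what happened.
2. Record relatedness as a separate eCRF field for all recorded AEs and SAEs, with relation to the study drug and relation to the assigned arm as distinct answers. Amend the eCRF sentence in 9.1.1 to match.
3. State in 9.2.5 that the underlying-disease exemption is applied without regard to arm.
4. Reconcile the deadlines in 9.3.2 and 9.3.5 for SAEs that are neither fatal nor immediately life-threatening. The sponsor decides which applies, or explains why the form and the report have different limits.

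The cost is wording in section 9, one eCRF field with its guidance, and modestly more AE entries for 52 patients. Sample size, visits and treatment do not change.
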